The MSQOL-54 is a comprehensive health-related quality of life measure incorporating general and MS-specific questions into a single instrument. The developers used the SF-36 as a base and added 18 questions to address MS-specific problems, including fatigue and cognitive function. This 54-item questionnaire provides 12 subscales, two summary scores, and two extra single-item measures. The subscales are physical function, role limits-physical, emotional role restrictions, pain, emotional well-being, energy, health perceptions, social position, cognitive function, health distress, overall quality of life, and sexual function (National Multiple Sclerosis Society, 2021).

The Barthel Index

When it comes to patients with chronic, debilitating illnesses, the Barthel index is an ordinal scale that evaluates functional independence in the domains of personal care and mobility. A total of ten variables describing activities of daily living and mobility are considered, with a higher number reflecting better capacity to operate independently. The Barthel Index assesses the level of help needed by a person on a set of ten activities of daily living (ADL) related to mobility and self-care (Elite Learning, 2008).

9-Hole Peg test

The 9-HPT is a short, standardized upper extremity exam. In MS research, gait analysis has been given precedence over arm and hand function analysis. In recent years, clinical investigations have increasingly recognized the value of assessing arm and hand function, particularly in severely disabled patients. The 9-HPT has recently become one of the most widely utilized upper extremity measurements in MS. Many qualified examiners can administer the 9-HPT since it is short and standardized. (National Multiple Sclerosis Society, 2021).

PHQ-9 (Patient Health Questionnaire-9)

Suicide prevention programs may also have a clinical component, which refers to how individuals are evaluated and treated for mental health problems or suicidal thoughts in medical facilities. The PHQ-9 is the most used depression and suicidal thoughts screening test. Other

screening methods exist, although some are tailored to certain populations or situations. The Patient Health Questionnaire (PHQ) is a self-administered version of the PRIME-MD diagnostic tool for common mental illnesses (Kroenke, 2001).

Physical Examinations

A complete physical examination will be performed by the principal investigator or delegated sub-investigator, including general appearance, head, eyes, ear, nose, and throat (HEENT), neck, cardiovascular, thorax/lungs, abdomen, genitourinary, musculoskeletal, lymph nodes, skin, neurological and mental status examination, height (at Screening only), and body weight at Visits 1, 2, 3, 4, 5, 6, 7, 8 and 9.

The principal investigator or delegated sub-investigator will evaluate the clinical significance of abnormal findings identified during physical examinations. Pre-existing conditions diagnosed through assessments and examinations at the screening visit or during the screening period are not adverse events but are recorded as medical history. If any clinically significant abnormal findings are discovered after informed consent or any pre-existing conditions worsen during the trial, these must be recorded as adverse events.

Vital Signs

Vital signs will be measured at Visits 1, 2, 3, 4, 5, 6, 7, 8 and 9 and will include respiratory rate, pulse rate, blood pressure (measured after the study participant has been in a seated position for more than 5 minutes of rest), body temperature and oxygen saturation. Clinical significance of any abnormal result must be evaluated by principal investigator. Clinically significant abnormal findings will be reported as adverse events.

Clinical Safety Laboratory Parameters

The following laboratory parameters should be collected at Visit 1, 2, 6 and 9.

- Comprehensive Metabolic Panel, also known as CMP or Chemistry Panel is a group of different tests that measure several substances in the study's participant blood. The following tests are included in this panel:

Comprehensive Metabolic Panel (CMP)	Reference Range	Units
GLUCOSE	70-99	MG/DL
BUN	6-20	MG/DL
CREATININE	0.60-1.30	MG/DL
eGFR AFRICAN AMER.	>60	ML/MIN/1.73
eGFR NON-AFRICAN AMER.	>60	ML/MIN/1.73
CALC BUN/CREAT	6-28	Ratio
SODIUM	133-146	MEQ/L
POTASSIUM	3.5-5.4	MEQ/L
CHLORIDE	95-107	MEQ/L
CARBON DIOXIDE	19-31	MEQ/L
CALCIUM	8.5-10.5	MG/DL
PROTEIN, TOTAL	6.1-8.3	G/DL
ALBUMIN	3.5-5.2	G/DL
CALC GLOBULIN	1.9-3.7	G/DL
CALC A/G RATIO	1.0-2.6	Ratio
BILIRUBIN, TOTAL	<=1.2	MG/DL
ALKALINE PHOSPHATASE	40-114	U/L
AST	9-40	U/L
ALT	5-40	U/L

- Complete Blood Count, also known as CBC, hemogram or CBC with Differential is a group of tests that evaluate the cells that circulate in blood, including red blood cells (RBCs), white blood cells (WBCs), and platelets.

CBC with manual differential	Reference Range	Units
WBC	3.5-11.0	K/UL
RBC	3.80-5.40	M/UL
HEMOGLOBIN	11.5-15.5	G/DL
HEMATOCRIT	34.0-45.0	%
MCV	80.0-99.0	fL
MCH	25.0-33.0	PG
MCHC	31.0-36.0	G/DL
RDW	11.5-15.0	%
NEUTROPHILS	40.0-75.0	%
LYMPHOCYTES	20.0-45.0	%
MONOCYTES	4.0-12.0	%
EOSINOPHILS	0.0-7.0	%
BASOPHILS	0.0-2.0	%
PLATELET COUNT	130-400	K/UL
ABSOLUTE NEUTROPHILS	1.50-7.50	K/UL
ABSOLUTE LYMPHOCYTES	1.00-4.00	K/UL
ABSOLUTE MONOCYTES	0.20-1.00	K/UL
ABSOLUTE EOSINOPHILS	0.00-0.50	K/UL
ABSOLUTE BASOPHILS	0.00-0.20	K/UL

- Coagulation Tests including Prothrombin Time (PT or PT-INR) to identify any coagulation disorder during study participation.

Coagulation	Reference Range	Units
Prothrombin Time (PT)	12.5-14.7	Seconds
INR	2.0-3.0	N/A
Partial thromboplastin time (PTT)	25.2-40.0	Seconds

- Urine Pregnancy Test, a urine sample, preferably collected during morning time, to confirm pregnancy during study participation. This test will be limited to Women of Childbearing Potential (WOCBP).

Pregnancy Test	Reference Range	Units
Urine Pregnancy Test	Positive - Negative	N/A

Other Assessments

Demography

Demographic data will be collected at the Screening Visit, including age, race, ethnicity, date of birth and gender.

Medical and Surgical History

Medical information on any previous concomitant illnesses, other than Multiple Sclerosis should be collected during Screening Visit and updated if needed during the following study visits. For planned procedures/hospitalizations during the clinical trial, documentation should be completed at the time of the Screening.

Multiple Sclerosis and Previous Therapy for this disease

The date of diagnosis of Multiple Sclerosis, as well as previous treatments, will be recorded during Screening visit.

Concomitant Medication Review

Data concerning concomitant medications and procedures will be collected throughout the clinical trial. This data will be obtained at scheduled or unscheduled visits based on information provided by the patient.

Handling of Biological Samples

Sampling tubes, material for shipments of the samples and a laboratory manual detailing all sample collection and shipment procedures will be provided and distributed to the clinical trial site by the selected laboratory. Laboratory samples will be collected as per protocol during Visit 1 – Screening, and/or Visit 2 – Infusion 1 (Baseline), Visit 6 - Infusion 5 and Visit 9 – End of Study.

Adverse Events

Definitions

Unanticipated Problems Involving Risk to Subjects or Others

Any incident, experience, or outcome that meets all the following criteria:

- Unexpected in nature, severity, or frequency (i.e., not described in study-related documents such as the IRB-approved protocol or consent form, the investigators brochure, etc.)
- Related or possibly related to participation in the research (i.e., possibly related means there is a reasonable possibility that the incident experience, or outcome may have been caused by the procedures involved in the research.)
- Serious (as defined below) ***“Serious” is different than “severe” as reported in the CTC criteria that applies a grade to the AE.***

Adverse Event

An ***adverse event*** (AE) is any symptom, sign, illness, or experience that develops or worsens in severity during the study. Intercurrent illnesses or injuries should be regarded as adverse events. Abnormal results of diagnostic procedures are adverse events if the abnormality:

- results in study withdrawal
- is associated with a serious adverse event
- is associated with clinical signs or symptoms
- leads to additional treatment or to further diagnostic tests
- is considered by the investigator to be of clinical significance

Serious Adverse Event

Adverse events are classified as serious or non-serious. A ***serious adverse event*** is any AE that is:

- fatal
- life-threatening
- requires or prolongs hospital stay
- results in persistent or significant disability or incapacity
- a congenital anomaly or birth defect
- an important medical event

Important medical events are those that may not be immediately life threatening but are clearly of major clinical significance. They may jeopardize the subject and may require intervention to prevent one of the other serious outcomes noted above. For example, drug overdose or abuse, a seizure that did not result in in-patient hospitalization, or intensive treatment of bronchospasm in an emergency department would typically be considered serious.

All adverse events that do not meet any of the criteria for serious should be regarded as ***non-serious adverse events***.

Adverse Event Reporting Period

The study period during which adverse events must be reported is normally defined as the period from the initiation of any study procedures to the end of the study treatment follow-up. For this study, the study treatment follow-up is defined as approximately 20 weeks following the last administration of study treatment.

Recording of Adverse Events

At each contact with the subject, the investigator must seek information on adverse events by specific questioning and, as appropriate, by examination. Information on all adverse events should be recorded immediately in the source documents and CRF and in the appropriate adverse event section of the source documents. All clearly related signs, symptoms, and abnormal diagnostic procedures results should be recorded in the source document and CRF, though should be grouped under one diagnosis.

All adverse events occurring during the study period must be recorded. The clinical course of each event should be followed until resolution, stabilization, or until it has been determined that the study treatment or participation is not the cause. Serious adverse events that are still ongoing at the end of the study period must be followed up to determine the outcome. Any serious adverse event that occurs after the study period and is possibly related to the study treatment or study participation should be recorded and reported immediately.

Reporting of Serious Adverse Events and Unanticipated Problems.

Investigator and the Sponsor must follow reporting timelines if any Serious Adverse Event or Unanticipated Problem occurs to the subject. Also, if any of them have the following criteria, it must be reported in a timely manner:

- related to study participation
- unexpected
- serious or involve risks to subjects or others

This report should include the minimum necessary information provided in the following table:

Stopping Rules

Infusion Stopping Rules

Study treatment infusion will be stopped if a least one of the following events occur:

1. Allergic reaction as evidenced by severe dyspnea (defined as intense tightening of chest, air hunger, breathlessness or feeling of suffocation), bronchospasm (defined as coughing, wheezing, difficulty breathing) or hypoxia (defined as pulse oximeter reading of less than 90%) after the product has been administered intravenously.
2. Patient verbally decline the treatment at any moment prior, or during the infusion.
3. Hyperpyrexia develops after infusion administration begins (core body temperature greater than or equal to 104°F).
4. Principal Investigator may stop the infusion at any time, based upon PI's discretion.
5. Malignant Hypertension (180/120 mm/Hg)
6. Sudden Severe Hypotension (30-40 mm/Hg drop from pre-infusion level)

If an infusion is stopped for a subject due to an adverse event or serious adverse event, including but not limited to hypersensitivity reaction/anaphylaxis, no additional study treatment will be given to the study participant who develops the event. Although, the study participant will not receive the investigational product, he or she must be followed for safety purposes according to the protocol.

Study Stopping Rules

This Clinical Trial will stop if any of the following events are present:

1. Subject's Death.
2. Occurrence of any thromboembolic event during or after HB-adMSCs administrations (up to 72 hours).
3. Any cerebrovascular ischemia or seizure event occurring within 72 hours after any of the investigational product administrations.
4. Any Serious Adverse Events determined to be related to the following:

- When there is one CTCAE.v5 grade 4 or 5 AE, irrespective of attribution.
- Either any CTCAE Grade 2 adverse event that persists for more than two weeks, or any Grade 3 adverse event, that occurs within 72 hours after product administration.

Should the study participant discontinue study treatment he/she will be followed for safety according to the protocol safety monitoring plan. The study participant will receive follow up communication via phone calls and/or electronically to ascertain the outcome until resolved fully. All will be documented as per protocol.

All changes to the study stopping rules shall be reviewed by FDA. If the study is suspended for any reason, it will not be re-opened until FDA agrees. Regardless of whether the study is stopped or suspended all subjects will be followed to the EOS as per protocol.

Statistical Methods

Sample size consists of up to 24 subjects who have been diagnosed with Relapsing Remitting Multiple Sclerosis. All data collected from subjects who are enrolled and received the investigational product will be analyzed. The incidence of Adverse Events and Serious Adverse Events will be recorded and reported. Efficacy will be measured by improvement of subject's signs and symptoms associated with Multiple Sclerosis. Interim analysis of all safety and efficacy data may be performed at any time deemed appropriate by the Sponsor. Although, the subject's data may be analyzed at any time, a data analysis of all available data will be conducted when a least 10 subjects in each group have completed Week 24. Data may be analyzed for internal informational purposes, reports, presentations, and manuscripts.

A repeat measure mixed model will be used to assess within-subject changes from baseline. correction for multiple comparisons will be employed for post-hoc comparisons. Multiple Sclerosis's assessment scores (i.e., MSQOL) at screening and infusion 1 (before treatment) will be averaged and treated as a baseline. Averaging is performed to minimize sources of variance (i.e., patient condition, assessors) and particularly to establish a reliable baseline from which to establish changes.

Data Handling

Case Report Forms (CRF)

As used in this protocol, the term CRF should be understood to refer to either a paper form or an electronic data record or both. Reports received by the site, or from the central laboratory should be printed, retained as source documentation, and signed by the principal investigator, indicating which values are considered clinically significant and to be reported as AEs if applicable.

The completion, review, and approval of all CRFs, as well as the completeness and authenticity of all clinical and laboratory data entered on these CRFs, are always the PI's personal responsibility. Signature of Principal Investigator will be required to attest that the information contained on the CRFs is accurate.

Original CRFs should not be made available in any form to third parties, except for authorized representatives of Hope Biosciences Stem Cell Research Foundation or appropriate regulatory authorities, without written permission from Hope Biosciences Stem Cell Research Foundation.

Changes in the Conduct of the Clinical Trial

Protocol Amendments

Any change to the protocol will need to have a protocol amendment submitted to the IND, and FDA and IRB must agree prior to proceeding.

Premature Clinical Trial Termination

Both the Study Investigator and Sponsor have the right to terminate the clinical trial at any time. Should this become necessary, the procedures will be agreed upon after consultation between the two parties. In terminating the clinical trial, the Sponsor and the Study Investigator will ensure that adequate consideration is given to the protection of the best interests of the study participants. Regulatory authorities and IRB will be informed.

In addition, the Sponsor reserves the right to terminate the participation of any clinical trial site. Conditions that may warrant termination include, but are not limited to:

- Insufficient adherence to protocol requirements
- Failure to enter patients at an acceptable rate

Reporting and Publication

Neither the complete nor any part of the results of the study carried out under this protocol, nor any of the information provided by the sponsor for the purposes of performing the study, will be published, or passed on to any third party without the consent of the study sponsor. Any investigator involved with this study is obligated to provide the sponsor with complete test results and all data derived from the study.

Archiving

Investigator File

The study investigator is responsible for maintaining all the records (protocol and protocol amendments, completed source and case report documents, signed informed consent forms, relevant communications, and all other supporting documents) which allow to conduct the clinical trial at the site in compliance with ICH-GCP. The study site should retain such documents until at least 2 years after the last approval of a marketing application or at least 2 years after the formal discontinuation of clinical development of the investigational product. These documents should be retained for a longer period if required by the applicable regulatory requirements in which the study is being conducted. Patient identification codes (patient names and corresponding study numbers) will be retained for this same period. The Investigator must contact Sponsor prior to disposing of any study records.

Trial Master File

The Sponsor will archive the Trial Master File in accordance with ICH-GCP and applicable regulatory requirements.

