- Incidence and risk of AEs of special interest (serious or nonserious), including thromboembolic events, peripheral events defined as, thromboembolism of the extremities, also infections and hypersensitivities.
- Clinically significant changes in laboratory values, vital signs, weight, and physical examination results.

Secondary Endpoints

The safety and efficacy endpoints of this study will be evaluated by identifying changes from Baseline to Week 52 in the following:

- Expanded Disability Status Scale (EDSS)
- The Barthel Index
- 9-Hole Peg Test
- Patient Health Questionnaire (PHQ-9)
- Incidence of treatment-emergent Adverse Event (TEAEs) and serious Adverse Events (SAEs).
- Incidence and risk of AEs of special interest (serious or nonserious), including thromboembolic events, peripheral events defined as, thromboembolism of the extremities, also infections and hypersensitivities.

- Clinically significant changes in laboratory values, vital signs, weight, physical examination results and Multiple Sclerosis concomitant medications.

Investigational Plan.

[figure not shown]
This is a randomized, double-blind, single center, phase 2 study to assess efficacy and safety of multiple HB-adMSCs vs. Placebo for the treatment of Multiple Sclerosis. The trial includes a screening period of up to 4 weeks, a 32-week treatment period, and a safety Follow-up period of 20 weeks after the last investigational product administration.

This clinical trial will be opened to enroll 24 eligible participants diagnosed with Multiple Sclerosis. Patients' recruitment will be conducted by the study team, if eligible participants are identified based on eligibility criteria, a screening visit will be scheduled. Informed consent form will be given to the study participants and signed before any study procedures. Informed consent form will include information about the clinical trial and some aspects should be considered during this process.

- Principal investigator and/or study team will make sure the participant was alert, and able to read and understand the language in the consent form.
- Principal investigator and/or study team will make sure the participant takes ample time to carefully read the consent form.
- Principal investigator and/or study team will make sure the consent form is carefully explained to the participant and any questions or concerns are addressed before signing the form.

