- Visit 8 – Safety Follow Up: approximately 42 weeks after the initial investigational product administration, active study participants will complete a follow up visit at the clinic site.
- Visit 9 – End of Study, during this final visit (approximately 52 weeks after Week 0) a complete group of study assessments will be performed to evaluate the safety and efficacy of HB-adMSCs or Placebo administrations.

Clinical assessments of disease activity will take place during the following visits:

- Visit 1 – Screening
- Visit 2 – Infusion 1 (**Baseline**)
- Visit 4 – Infusion 3
- Visit 6 – Infusion 5
- Visit 8 – Follow Up
- Visit 9 – End of Study

Blood samples for safety assessments will be collected in as follows:

- Visit 1 – Screening: after informed consent has been obtained, blood samples should be collected from a vein of the study's participant arm, these lab results will help assess the subject's eligibility.
- Visit 2 – Infusion 1, (**Baseline**): safety laboratory samples will be collected from the study participant's vein to establish a baseline for comparison with the laboratory results obtained in subsequent visits.
- Visit 6 – Infusion 5: safety laboratory samples should be collected from a vein of the study's participant arm during this visit.

Visit 9 – End of Study: safety laboratory samples should be collected from a vein of the study's participant arm during this visit.

For study participants who do not complete the study trial, a safety follow-up visit will be scheduled as follows:

- For subjects who did not receive any of the investigational products and were eligible to participate in the trial, they will be invited to a safety follow-up visit, or Early termination visit (ETV) within 30 days after the last visit.
- For subjects who received at least one dose of the investigational product, they will be invited to a safety follow-up visit, approximately 30 days following that single treatment.
- For subjects who received more than one dose of the investigational product, they will be invited to a safety follow-up visit, approximately 30 days following the last treatment.

Withdrawal Criteria

In different situations, a study subject may withdraw from the study before the planned completion of the visits. One of these situations is mentioned below,

1. Voluntary withdrawal: subject doesn't want to continue receiving the investigational product.

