The principal investigator and designated staff must record the reason for the subject's withdrawal on the case report forms, specifically in the Early Termination Visit and /or a Note to File Form.

Study participants discontinued from the clinical trial who received at least one infusion (HB-adMSCs or placebo) will be invited to a Safety Follow-up visit approximately 30 days after that single infusion.

Any withdrawal must be documented in the source documents and electronic case report forms. If the reason for the discontinuation is an adverse event or serious adverse event, the event must be followed until resolution by the principal investigator.

The Sponsor may temporarily or permanently discontinue the clinical trial at any time for safety, ethical, compliance or other reasons. Study's principal investigator and regulatory authorities will be notified about this decision and the reason of it.

Selection of Clinical Trial Population

Clinical Trial Population

This clinical trial is designed to include adult male and female outpatients with Relapsing Remitting Multiple Sclerosis. Study participants who fulfil all the inclusion criteria and none of the exclusion criteria are eligible for participation in the clinical trial. See below eligibility criteria:

Eligibility Criteria

Inclusion Criteria

A study participant will be eligible for inclusion in this study only if all the following criteria apply:

1. Male and female participants 18 – 75 years of age.
2. Study participants must have been diagnosed with Relapsing Remitting Multiple Sclerosis (RRMS) for at least 6 months before study participation.
3. Study participants must be stabilized on any MS therapy for at least 6 months prior to randomization.
4. Study participants must agree not to increase or begin any Diseases Modifying Therapies for MS during participation in the clinical trial.
5. Study participants must have an EDSS score between 3.0 to 6.5. (Patient must be able to walk).
6. Study participants must have previously banked their mesenchymal stem cells with Hope Biosciences.
7. Study participants should be able to read, understand and to provide written consent.
8. Before any clinical-trial-related procedures are performed, informed consent must be obtained from the participants voluntarily.
9. Female study participants should not be pregnant or plan to become pregnant during study participation and for 6 months after last investigational product administration. *

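### Participants who decline further infusions are handled as study withdrawals with one visit at about 30 days, so their Week 52 MSQOL-54 is not assured and the safety periods conflict

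*Protocol*

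**What the plan says.** **Leaving the study.** The protocol's Withdrawal Criteria describe withdrawal from the study before the planned visits are complete, and list one situation as an example: "Voluntary withdrawal: subject doesn't want to continue receiving the investigational product". The same section later mentions an adverse event as another possible reason for discontinuation.

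**What happens next.** The Investigational Plan gives non-completers who received more than one dose a single safety visit "approximately 30 days following the last treatment". The Withdrawal Criteria say that anyone discontinued from the trial after at least one infusion "will be invited to a Safety Follow-up visit approximately 30 days after that single infusion". Table 4 has no early-termination column, and the visit descriptions list no procedures for such a visit. At Week 42, "active study participants will complete a follow up visit at the clinic site"; the word active is not defined.

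**Safety periods.** The Investigational Plan describes "a safety Follow-up period of 20 weeks after the last investigational product administration". Under Adverse Event Reporting Period, "the study treatment follow-up is defined as approximately 20 weeks following the last administration of study treatment". SAP Section 5.3.2.2 closes the treatment-emergent window at Week 42 or early withdrawal.

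**Stopping rules.** A participant whose infusion is stopped for an adverse event receives no more product but stays in safety follow-up. Participants who discontinue treatment are followed for safety, by phone or electronically, until the outcome resolves. The sentence that "all subjects will be followed to the EOS as per protocol" covers the case where the whole study is stopped or suspended.

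**Analysis.** The SAP's primary analysis is an ANCOVA of change in MSQOL-54 composite scores at Week 52 (Section 5.2.2). Its efficacy set admits only participants who received all six infusions (Section 4). The protocol's Statistical Methods say that all data from enrolled participants who received product will be analysed.

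**The concern.** Stopping treatment and leaving the study are different events. A participant may refuse further infusions and still be willing to complete a questionnaire at Week 52. The Withdrawal Criteria give no route for that person.

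Stopping may be related to tolerability or to lack of perceived benefit, so those without a Week 52 score may not be a random subset. With about 12 participants per arm, each one lost is about 8% of an arm (1/12). The loss is also permanent: an analysis set can be redefined before database lock, but a Week 52 score that nobody collected cannot be recovered.

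On safety, an early stopper has follow-up of a different length depending on which section the site reads.

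**Working it through.** **Step 1: reproduce the plan's own period.** The last infusion is at Week 32 and the end of study is at Week 52. 52 − 32 = 20 weeks = 140 days, which matches the stated 20 weeks.

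**Step 2: compare it with the exit visit.** 30/140 = 0.214, or 21% of the period. The shortfall is 140 − 30 = 110 days (15.7 weeks).

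**Step 3: locate the exit visit for early stoppers.** 30 days is 30/7 = 4.3 weeks. For a last infusion at Week w, the exit visit falls at w + 4.3, the 20-week period ends at w + 20, and the time from exit visit to Week 52 is 52 − w − 4.3. Table 4 schedules MSQOL-54 at Weeks 0, 8, 24, 42 and 52. The last column counts only post-baseline scores from visits at which the participant was infused.

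| Last infusion | Week w | Exit visit (week) | 20-week period ends (week) | Weeks from exit visit to Week 52 | Post-baseline MSQOL-54 |
|---|---|---|---|---|---|
| 1 | 0 | 4.3 | 20 | 47.7 | none |
| 2 | 4 | 8.3 | 24 | 43.7 | none |
| 3 | 8 | 12.3 | 28 | 39.7 | Week 8 |
| 4 | 16 | 20.3 | 36 | 31.7 | Week 8 |
| 5 | 24 | 28.3 | 44 | 23.7 | Weeks 8 and 24 |

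The 20-week period itself ends before Week 52 in every row. Aligning the safety periods would therefore not secure the primary outcome, which needs its own rule.

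**Step 4: the third end of follow-up.** For a participant who receives all six infusions, the SAP's Week 42 cut-off is 42 − 32 = 10 weeks after the last infusion, half of the protocol's 20. For an early stopper it is the withdrawal date.

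**Step 5: how many participants.** The documents give no dropout rate, so 10% to 20% is an assumption. 0.10 × 24 = 2.4 and 0.20 × 24 = 4.8, or about 2 to 5 participants, if each one who stops also leaves.

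**Step 6: would either remedy work alone?** Changing only the efficacy set would admit early stoppers without a Week 52 score. Collecting only the Week 52 score would yield data that the six-infusion rule then excludes. Both are needed.

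**The case against.** The best defence is that the protocol does partly separate stopping treatment from leaving. Its stopping rules keep participants who discontinue treatment in safety follow-up, and the 30-day visit is written for those who do not complete, or are discontinued from, the trial. A 20-week period for those who stay can coexist with an exit visit for those who leave.

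This defeats several stronger readings that a reader might infer:

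- *Everyone who stops infusions leaves the study.* The stopping rules say otherwise for safety, and the Withdrawal Criteria offer their listed situation only as an example.
- *Week 52 scores for stoppers are never collected.* Nothing forbids collecting them. What is missing is any provision that they will be.
- *No analysis of all randomised or all treated participants is possible.* The SAP's repeated-measures model can use available post-baseline scores, so Weeks 8 and 24 could support a likelihood analysis under missing-at-random. That is weaker than observed outcomes, does not help those who leave before Week 8, and is currently blocked by the six-infusion set.
- *Late adverse events are lost altogether.* An event that causes discontinuation is followed to resolution, and possibly related serious events after the study period are still reported. The exposure is to new late events outside those two provisions, chiefly non-serious ones.

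The defence does not close the gap. The stopping rules promise safety follow-up and list no efficacy assessments. Their follow-up to end of study applies when the trial halts, not when one participant declines an infusion. The Adverse Event Reporting Period makes no exception for people who leave.

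**Conclusion.** The point holds for participants who decline further infusions. The protocol classes them as withdrawing, provides one safety visit at about 30 days, and nowhere assures their Week 52 MSQOL-54. For those stopping after infusions 1 to 5, that visit falls 23.7 to 47.7 weeks before Week 52.

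The 30-day visit does not fit the 20-week adverse event period (21% of it), and the SAP's cut-off adds a further inconsistency.

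The figure of about 2 to 5 of 24 rests on the assumed 10% to 20% rate and on every stopper leaving, which the documents do not say. At those numbers, 8% to 21% of the planned sample (2/24 to 5/24) would lack the primary outcome, possibly not at random. The sponsor should correct this.

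**What to change.** 1. In the Investigational Plan and Withdrawal Criteria, define stopping infusions and withdrawing consent to follow-up as separate events, each with its own record of date and reason.
2. Invite participants who stop infusions but still consent to the remaining scheduled efficacy assessments in Table 4 through Week 52. The documents describe MSQOL-54 only at clinic visits, so the cost should be planned on that basis.
3. Change the efficacy set in SAP Section 4 so that these data enter the primary analysis. This would also bring the SAP into line with the protocol's statement on analysing all treated participants.
4. Reconcile the follow-up and adverse event periods across the Investigational Plan, Withdrawal Criteria, Adverse Event Reporting Period, stopping rules and SAP Section 5.3.2.2. This review does not propose a length.

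The cost is one protocol amendment, one SAP amendment, and a few extra visits for the small number who stop early.
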